2.0 Purpose

The overall goal of this study is to identify the priorities of individuals living with COPD in terms of their activities and participation, as well as their research priorities and health care concerns. To achieve this overall goal, the study is divided into three phases (see Figure 1). The purpose of the *first phase* is to develop and pilot test a questionnaire created for individuals living with COPD to assess their activities, participation, and health care and COPD-related research priorities. The Activities, Healthcare and Research Priorities Questionnaire (AHRPQ) was developed based on past research, then verified by a panel of COPD and participation experts to gather their opinions and recommendations. The AHRPQ was then examined by adults with COPD in focus groups, where they provided feedback on the content and readability of the questionnaire. Five focus group participants were also invited to complete the full survey online as an initial pilot test.

The purpose of the *second phase* of the study is to compare across diagnosed COPD stages and disease severity the extent to which adults with COPD participate in the listed activities and identify their primary research and health-care related priorities. The AHRPQ will be administered at three sites across Montreal where clinical data for each participant will be available. This phase will also help establish the reliability of the questionnaire.

In the *third phase*, the purpose is to administer the questionnaire to a pan-Canadian sample to identify the activities that individuals living with COPD participate in, the barriers that limit their participation in these activities, the activities that are of most importance for this population, and their health concerns and research priorities. We will also be examining the relationship between participation and quality of life related outcomes. The questionnaire will be distributed to a larger population of individuals living with COPD who self-report their COPD diagnostic/severity.

This amendment is to add the protocol for the *second phase* of the study. We presented the overall goal in order to contextualize the current application.

[figure not shown]

Figure 1: The three phases of the study, broken down into each step of the phases. The identified phase (Phase 2) is the following protocol amendment.

References

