Descriptive statistics were used to report individuals' daily and social participation and provide a picture of how respondents participated in each activity. The distribution of the scores for each activity was assessed based on quartiles of airflow obstruction, breathlessness burden and exacerbation risk, sex, age, and PR participation status. Using IBM SPSS Statistical software (v.23), chi-square analysis, with standardized residuals post-hoc analyses, were performed on the participation items individually to determine if the observed value differed from the statistically expected value for quartiles of airflow obstruction, breathlessness burden and exacerbation risk, sex, age, and PR participation status. To examine the barriers and facilitators to participation, descriptive statistics were used to identify the most common barrier/facilitator. A repeated measures analysis of variance (ANOVA) was used to determine if there was a significant difference between the barrier/facilitator that was selected the most often compared to all other barriers/facilitators.

Descriptive statistics were used to report individuals' healthcare and research priorities. The distribution of the scores for each activity was assessed based on quartiles of airflow obstruction and exacerbation burden and exacerbation risk. Using IBM SPSS Statistical software (v.23), chi-square analysis, with standardized residuals post-hoc analyses, were performed to determine if the observed number of responders for each healthcare and research topics differed

from the statistically expected value for airflow obstruction and exacerbation burden and exacerbation risk. Additionally, non-parametric tests were conducted to determine if there were any between group differences for the healthcare and research topics and airflow obstruction and exacerbation burden and exacerbation risk groups. A Kruskal-Wallis non-parametric test was conducted due to the non-normality of the data, as the mean for both healthcare and research topics was skewed. Individuals giving 10% of their time/funding was the most common response for each of the healthcare or research topics. Post-hoc analyses with Bonferroni corrections were also conducted.

For the secondary outcomes, one-way ANOVAs were used to determine mean group differences. However, for both FEV1% predicted and physical activity levels, a Kruskal-Wallis non-parametric test was conducted as the data was non-normal.

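### Phase 2 aims to identify primary healthcare and research priorities, but the SAP specifies no topic-to-topic comparison and no interval for any topic

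*SAP*

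**What the plan says.** **Aim.** Protocol section 2.0 (Purpose) states an overall goal that covers participation "as well as their research priorities and health care concerns". For Phase 2 it names a comparison of participation across COPD stage and severity, and also the task to "identify their primary research and health-care related priorities".

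**Analysis of topics.** The SAP (Statistical Analysis) begins: "Descriptive statistics were used to report individuals' healthcare and research priorities". It does not say which statistics. It then names:

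- a chi-square analysis of whether the number of responders per topic departs "from the statistically expected value for airflow obstruction and exacerbation burden and exacerbation risk";
- a second step in which "non-parametric tests were conducted to determine if there were any between group differences for the healthcare and research topics" across the severity groups, by Kruskal-Wallis;
- a closing line, directly after the Kruskal-Wallis text: "Post-hoc analyses with Bonferroni corrections were also conducted". The contrasts and their number are not given.

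**Typical answer.** The SAP adds that "Individuals giving 10% of their time/funding was the most common response for each of the healthcare or research topics".

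**Barriers and facilitators.** In the same section, a repeated measures ANOVA looks for a "significant difference between the barrier/facilitator that was selected the most often compared to all other barriers/facilitators".

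**The concern.** To call a topic primary is to say that it stands above other topics in the eyes of the same respondents. That is a within-person comparison of topics. The planned tests answer a different question: whether a given topic's share differs by airflow-obstruction quartile or by breathlessness and exacerbation group.

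Topic means from any finite sample fall in some order, whether or not that order would recur in another sample. Without an interval or a paired comparison, a reader cannot tell a clear leader from a group of topics that the data do not separate. Protocol section 2.1 (Expected Outcomes) intends the findings to steer what providers tell patients and what researchers study, so this distinction matters to those who use the results.

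**Working it through.** **1. What each analysis compares**

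| Analysis in the SAP | Compares | Can it place one topic above another? |
|---|---|---|
| Descriptive statistics on topics | nothing formally; statistics not named | gives estimates, with no stated precision |
| Chi-square on responders per topic | severity groups | no |
| Kruskal-Wallis on topics | severity groups | no |
| Bonferroni post-hoc | follows the Kruskal-Wallis; no topic contrast named | no |
| Repeated measures ANOVA | leading barrier/facilitator against the others | yes, but not applied to topics |

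The chi-square wording is loose, but its expected value is defined by severity group, so it is still a between-group test.

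**2. Is there a figure to reproduce?** No. The documents give no sample size, alpha, power, number of topics, mean or SD for this analysis. Everything below rests on assumed inputs and shows only how such data behave.

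**3. Can the between-group test stand in?** Assume 200 respondents in four groups of 50 and 10 topics. Let one topic have a true share of 30% and the other nine (100 − 30)/9 = 7.8% each, the same in every group. Kruskal-Wallis on the dominant topic rejected in 4.5% of 1,000 runs, which is its null rate at the 5% level. A topic nearly four times as large as the rest (30/7.8 = 3.8) leaves no trace in that test.

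**4. How much order can chance produce?** Assume 10 topics, allocations that sum to 100% (Dirichlet), SD 5 or 10 points per topic, and N = 50, 100 or 200 (1,500 runs each).

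- *All topics truly equal.* The average gap between the highest and lowest observed means is 2.2 / 1.6 / 1.1 points at N = 50 / 100 / 200 with SD 5, and 4.6 / 3.3 / 2.3 points with SD 10.
- *One topic at 11%, the other nine at 10 − 1/9 = 9.9%.* The true leader is observed first in 48% / 69% / 88% of samples with SD 5, and in 26% / 35% / 48% with SD 10.

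Wider true gaps would raise these rates.

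**5. What would a paired comparison resolve?** SE of a difference between two topic means = SD × √(2(1 − ρ)/N). With K = 10 and a fixed sum, ρ = −1/(K − 1) = −1/9.

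Example, N = 100 and SD 5: 5 × √(2 × 1.111/100) = 0.75, so the 95% half-width is 1.96 × 0.745 = 1.46 points. All pairs number 10 × 9/2 = 45.

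| SD | N | 95% half-width | Half-width, Bonferroni over 45 pairs |
|---|---|---|---|
| 5 | 50 | 2.07 | 3.44 |
| 5 | 100 | 1.46 | 2.43 |
| 5 | 200 | 1.03 | 1.72 |
| 10 | 50 | 4.13 | 6.87 |
| 10 | 100 | 2.92 | 4.86 |
| 10 | 200 | 2.07 | 3.44 |

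With equal topics, the Friedman test rejected in 3.5% to 5.2% of 400 runs. With the 11% leader, it rejected in 10% / 23% / 40% (SD 5) and 6% / 9% / 14% (SD 10). A non-significant result would therefore not show that topics are equal.

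**The case against.** **Comparing across severity may be the whole aim.** The Phase 2 sentence opens with comparison across stage and severity, and that phrase can be read as governing the priorities too. The between-group tests fit that reading. Phase 3, the pan-Canadian sample, is also given the task of identifying priorities. This shows that the between-group tests have a proper purpose. It does not remove the separate instruction to identify primary priorities in Phase 2.

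**The SAP promises no ranked list.** This is correct. A reader might infer that the study will publish a ranking with no measure of uncertainty. The SAP does not use the word, and its unspecified descriptive statistics could include SDs, quartiles or intervals. What the documents support is narrower: no topic-to-topic comparison or interval is specified. An SD per topic would not fill the gap, because it is not a paired contrast.

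**The shared 10% answer proves little.** This also stands. A reader might infer that the topics are nearly equal. Topics with the same mode can have very different means and upper tails, and the sentence appears beside the explanation of skewness and the choice of Kruskal-Wallis.

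**Descriptive reporting is legitimate in a questionnaire study.** It is, and nothing here invalidates the survey. Descriptive estimates still need a stated precision if some are to be called primary, and the SAP itself goes beyond description for barriers and facilitators.

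**Conclusion.** The point holds as a gap between aim and analysis. Phase 2 is to identify primary healthcare and research priorities. The SAP describes the topics and tests them only between severity groups, while it does compare items within person for barriers and facilitators. Severity-group tests cannot show whether one topic outranks another, and a mode common to all topics cannot order them.

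This conclusion rests on the text, not on a number. A reader might take the simulated rates as the chance that this study names the wrong leading topic. The documents do not support that: the number of topics, their spacing, the SD, the sample size and the fixed-sum format are all assumed. The true gaps could be wide enough for the order to be beyond doubt.

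Label: cheap improvement.

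**What to change.** For each topic set (healthcare, research):

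- Report each topic's mean share with a 95% bootstrap interval, resampling participants, and a bootstrap interval for its rank.
- Add a Friedman test across topics, with paired comparisons adjusted over all topic pairs. Adjusting only for the observed leader against the rest is not enough, because the leader is picked from the same data.
- Describe topics that cannot be separated as tied, and say that this means not distinguished rather than equal.
- Keep the severity-group tests for the aim they serve.

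Re-ranking without respondents who gave every topic the same percentage is not worth adding. Each such person adds one constant to every topic total. Removing m of N people multiplies every difference between topic means by N/(N − m), so the order cannot change.

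The cost is a short added analysis on data already held, with no new participants. The downside is that fewer topics may be called a top priority.
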